#### **9.2.4 Change From Baseline in Visual Analogue Scale for Pruritus at Week 1, Week 4, and Week 8**

The change from baseline in visual analogue scale (VAS) for pruritus will be analyzed in the same manner as that in the overall EASI score or each EASI symptom score.

#### **9.2.5 Change From Baseline in VRS for Pruritus up to Day 7**

The change from baseline in VRS for pruritus up to Day 7 will be analyzed in the same manner as that in overall EASI score or each EASI symptom score. Data will be collected

at baseline, 4, 8, and 12 hours after the start of administration, 1 day after the start of administration (morning and night), and thereafter in the same manner up to Day 7 (morning). The same analysis will be performed by the time zone of assessment (morning or evening). Morning or evening will be determined based on the time label entered in the case report form (CRF), not using the timepoints defined in Table 6.4-2, except the baseline, which is irrespective of the time zone of assessment. Data will be collected at baseline, and the timepoints specified above on Day 1 to Day 7.

#### **9.2.6      Change From Baseline in Dermatology Life Quality Index Score at Week 1, Week 4, and Week 8**

The change from baseline in Dermatology Life Quality Index (DLQI) score will be analyzed in the same manner as that in the overall EASI score or each EASI symptom score. The DLQI scores will be classified into the following categories and a shift table at baseline, Week 1, Week 4, and Week 8 will be created.

DLQI score categories: 0 to 1, 2 to 5, 6 to 10, 11 to 20, and 21 to 30

#### **9.2.7      Change From Baseline in Patient-Oriented Eczema Measure Score at Week 1, Week 4, and Week 8**

The change from baseline in Patient-Oriented Eczema Measure (POEM) score will be analyzed in the same manner as that in the overall EASI score or each EASI symptom score.

#### **9.2.8      Change From Baseline in Overall Percentage Affected BSA at Week 1, Week 4, and Week 8**

The change from baseline in overall percentage affected BSA will be analyzed in the same manner as that in the overall EASI score or each EASI symptom score.

#### **9.2.9      Percent Changes From Baseline in Overall EASI Score, EASI Symptom Scores, VAS for Pruritus, DLQI, and POEM Scores at Week 1, Week 4, and Week 8**

The percent changes from baseline in overall EASI score, EASI symptom scores, EASI scores for body regions, VAS for pruritus, DLQI score, and POEM score will be

analyzed at Week 1, Week 4, and Week 8 (as well as Week 2 and Week 6), in the same manner as the changes from baseline in the respective scores.

#### **9.2.10 Time to Response in IGA**

For the time to response in IGA (days to the first response in IGA in each subject), a cumulative response rate will be computed by each treatment group using the Kaplan-Meier method and plotted. At each timepoint, the number of subjects (at risk), the p-value of the log-rank test comparing the vehicle group and each OPA-15406 group, and the time until one half of the subjects have achieved a response (medial survival time [MST]) will be provided. Subjects with an IGA of 0 (clear) or 1 (almost clear) with an improvement by at least 2 grades from the baseline are defined as responders. The starting point is the baseline. Subjects who have failed to achieve a response will be treated as censored on the day of the final IGA assessment.

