6.4 Method of Minimizing or Avoiding Bias

This trial is a randomized, double-blind trial.

The IMP allocation manager will prepare a master “random allocation table” (hereinafter, “randomization table”) and conduct IMP coding according to the operating procedures for randomization. Also, the IMP allocation manager will prepare an emergency code list for use in emergencies such as the occurrence of a serious adverse event.

The investigator, subinvestigator, and subjects are blind to the IMP randomization code. Except for some designated personnel, the sponsor’s trial staff, including the personnel of contract research organizations, are also unable to access the IMP randomization code during the trial period.

Prior to the trial start and unblinding, the IMP allocation manager will confirm that the IMPs are indistinguishable. The randomization table is sealed by the IMP allocation manager just after completion of IMP randomization and it is kept under strict control until unblinding after fixation of all CRFs and the database.

The emergency code list will be kept under strict control by the registration system until the end of the trial. If a medical emergency occurs in a subject and knowledge of his or her IMP randomization code is considered important for treatment, the emergency code will be broken according to the “[8.2.4 Emergency Code Breaking \(Procedure for Unblinding During the Trial Period\)](#).”

When IMPs are recovered by the sponsor prior to unblinding, they are to be recovered sealed by the IMP allocation manager.

The subjects will be allocated to the 0.3% OPA-15406 group, the 1% OPA-15406 group, and the vehicle group in a ratio of 1:1:1 using dynamic allocation to ensure

balance within the trial sites and that of the baseline IGA (mild or moderate at the baseline examination).

The results of drug concentration measurements will not be revealed until unblinding at the end of the trial.

7 Observations/Examinations/Variables, Methods and Implementation Timings

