### 1) Screening period

After obtaining informed consent, the investigator or subinvestigator will perform a screening examination. The screening period is defined as the period between the day of the screening examination and the day of the baseline examination (2-30 days).

The subjects who meet the inclusion criteria and do not meet the exclusion criteria at the baseline examination will be dynamically allocated to the test product (0.3% or 1% formulation of OPA-15406) or the comparator (vehicle of OPA-15406), using the trial site and IGA at the baseline examination as the allocation factors.

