## 9.1 Primary Endpoint

The primary endpoint is incidence of success in IGA at Week 4.

Comparisons of incidences of success in IGA at Week 4 between the 1% OPA-15406 group and the vehicle group, and between the 0.3% OPA-15406 group and the vehicle group will be conducted using the Cochran-Mantel-Haenszel test stratified by baseline IGA score (mild or moderate). The closed testing procedure will be employed to avoid issue of multiplicity. When superiority of the 1% OPA-15406 group compared to the vehicle group is demonstrated with a two-sided significance level of 0.05, a comparison between the vehicle group and the 0.3% OPA-15406 group will be performed. The difference in incidence of success in IGA between each OPA-15406 group and the vehicle group and its two-sided 95% confidence interval (a Mantel-Haenszel estimator of the common risk difference and its two-sided 95% confidence interval) will be computed. Additionally, two-sided 95% confidence interval for the incidence of success in IGA in each treatment group will also be calculated using Clopper-Pearson method.

The SAS code to compare the incidence of success in IGA by the Cochran-Mantel-Haenszel test and to calculate the difference in incidence of success in IGA and its two-sided 95% confidence interval is shown below.

```
proc freq ;
  tables BaselineIGA *Treatment*Response/riskdiff(common) cmh ;
  run;
```

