## 9.2 Secondary Endpoints

### 9.2.1 Incidence of Success in IGA at Week 1 and Week 8

Incidence of success in IGA at Week 1 and Week 8 (as well as Week 2 and Week 6) will be analyzed in the same manner as described in [Section 9.1](#).

The change in incidence of success in IGA (the incidence of success in IGA in the primary analysis and the incidence of success in IGA defining responders as subjects with an improvement in IGA to 0 [clear] or 1 [almost clear]) will be plotted by timepoint for each treatment group.

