### **9.2.2 Change From Baseline in IGA at Week 1, Week 4, and Week 8**

Based on the OC data set, the change from baseline in IGA (at Week 1, Week 2, Week 4, Week 6, and Week 8; if the timing of discontinuation falls within the allowable window of a timepoint, the data at discontinuation will be included as the data for the timepoint) will be analyzed using the mixed-model repeated measures (MMRM) analysis with treatment (0.3% or 1% OPA-15406 groups, and vehicle group), timepoint, and interaction between treatment and timepoint as factors and baseline IGA as a covariate.

An unstructured covariance matrix will be used to model the within-subject errors and Kenward-Roger method will be used to calculate the standard error of fixed-effects and the degree of freedom. If the MMRM procedure fails to converge under unstructured covariance structure, the following structure will be used in the order of 1) heterogeneous toeplitz, 2) heterogeneous autoregressive of order 1, 3) heterogeneous compound symmetry, and the first (co)variance structure converging to the best fit will be used.

The least square mean of each treatment group will be calculated by timepoint. The difference in the least square mean between the vehicle group and each OPA-15406 group, and the two-sided 95% confidence interval and p-value will also be calculated at Week 1, Week 4, and Week 8 (as well as at Week 2 and Week 6). The least square mean and the standard error will be plotted by timepoint for each treatment group.

The SAS code to conduct the MMRM analysis is shown below.

```
proc mixed method = reml ;  
  class Treatment Visit Subject ;  
  model Change = Treatment Visit Treatment*Visit Baseline/s ddfm = kr ;  
  repeated Visit/type = un sub = Subject ;  
  lsmeans Treatment*Visit/pdiff cl alpha = 0.05 ;  
  run;
```

“Baseline” represents the IGA at baseline.

The SAS code to use when the MMRM procedure fails to converge under the unstructured covariance structure is shown below. (Designate *type* = *TOEPh* for heterogeneous toeplitz, *type* = *ARH*(1) for heterogeneous autoregressive of order 1, and *type* = *CSH* for heterogeneous compound symmetry).

```
proc mixed method = reml empirical ;  
  class Treatment Visit Subject ;  
  model Change = Treatment Visit Treatment*Visit Baseline/s ;  
  repeated Visit/type = TOEPh sub = Subject ;  
  lsmeans Treatment*Visit/pdiff cl alpha = 0.05 ;  
  run;
```

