Based on the OC and LOCF data sets, analysis of covariance (ANCOVA) model with treatment (0.3% or 1% OPA-15406 group, and vehicle group) as a factor and baseline IGA as a covariate will be applied to the change from baseline up to each timepoint. The least square mean of each treatment group will be calculated by timepoint. The difference in the least square mean between the vehicle group and each OPA-15406 group, and the two-sided 95% confidence interval and p-value will also be calculated at Week 1, Week 4, and Week 8 (as well as at Week 2 and Week 6). Based on the OC and LOCF data sets, measured values and changes from baseline in IGA at Week 1, Week 4, and Week 8 (as well as at Week 2 and Week 6) will be summarized by treatment group using descriptive statistics.

The mean with standard error of measured values (in the OC and LOCF data sets) will be plotted by timepoint for each group.

Shift tables will be created for the change from baseline in IGA (-3, -2, -1, ±0, +1, +2) at Week 1, Week 4, and Week 8.

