### **9.4 Adjustments for Covariates**

In the analysis of the incidence of success in IGA, the primary analysis, the Cochran-Mantel-Haenszel test stratified by baseline IGA (mild or moderate) will be conducted.

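### The log-rank test for time to IGA response could be stratified by baseline IGA, an allocation factor and the stratum for the same response elsewhere; the gain is optional and cannot be fixed from the documents.

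*SAP*

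**What the plan says.** SAP 9.2.10 plans Kaplan-Meier response curves by treatment group, numbers at risk, the median and "the p-value of the log-rank test comparing the vehicle group and each OPA-15406 group". No strata or covariates are named. A responder has IGA 0 or 1 with at least a two-grade improvement, and non-responders are censored at their last IGA assessment.

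Elsewhere the plan uses baseline IGA repeatedly:

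- **Allocation.** SAP 3 allocates subjects dynamically, "using the trial site and IGA at the baseline examination as the allocation factors". Protocol 6.4 says the same.
- **Response rate.** SAP 9.1 applies the CMH test, stratified by mild or moderate, to the same responder definition at Week 4. SAP 9.2.1 extends it to Weeks 1, 2, 6 and 8.
- **IGA change.** In SAP 9.2.2 the mixed model has "interaction between treatment and timepoint as factors and baseline IGA as a covariate". The analysis of covariance also has "baseline IGA as a covariate will be applied to the change from baseline up to each timepoint".

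The stated scope of adjustment is narrow. For the primary analysis, SAP 9.4 says "the Cochran-Mantel-Haenszel test stratified by baseline IGA (mild or moderate) will be conducted", and Protocol 11.3.8 likewise names only the CMH test. SAP 6.6.1 makes p-values outside the primary variable a reference indication without multiplicity adjustment. Protocol 11.3.1.2 planned only Kaplan-Meier plots for this variable, so the log-rank test is an SAP addition.

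**The concern.** Of the between-group tests on IGA, this is the only one that leaves baseline IGA out. The hurdle for response differs by stratum by definition: from a score of 2 the only qualifying result is 0, while from a score of 3 either 0 or 1 qualifies. Moderate subjects may therefore respond more often, although the documents report no response rates by baseline IGA, so this is likely and not shown.

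When allocation balances a prognostic factor and the test ignores it, the test's variance includes between-stratum variation that cannot contribute to the treatment difference. The test then rejects slightly too rarely under the null and loses some power.

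SAP 13.1 adds a point of consistency. It drops the protocol's logistic regression on baseline IGA and treatment, and cites the time-to-response analysis among the reasons that IGA is still adequately evaluated. That analysis does not adjust for baseline IGA; the CMH test and the mixed model cited with it do.

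At stake is the efficiency of one supplementary p-value per active group.

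**Working it through.** **The plan's own figure.** The documents give no power for the log-rank test. The stated 54 per group (Protocol 11.5, SAP 12.2) belongs to the primary endpoint at 20.93% vs 2.70%, and it reproduces: exact power of the two-sided Fisher test is 79.1% at 53 and 80.2% at 54 per group. Going from 54 to 60 implies a 10% allowance, since 54/60 = 0.90.

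**Response rates to enter.** A cumulative first-response rate by Week 8 cannot be lower than the rate at any single visit. From Protocol 1.2.2.4 (Week 4) and 1.2.3 (Week 8):

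- 1% group: max(20.93, 16.28) = 20.93%
- 0.3% group: max(14.63, 17.07) = 17.07%
- Vehicle: max(2.70, 10.81) = 10.81%

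**Stratum rates.** With mild share w and moderate-to-mild response ratio r, both assumed and equal across arms:

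p_mild = p / (w + (1 − w)·r), and p_moderate = r·p_mild.

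At w = 0.5 the divisor is 1.5, 2.5 or 4.5 for r = 2, 4 or 8. For example, at r = 4 the 17.07% becomes 6.83% mild and 27.31% moderate, and the 10.81% becomes 4.32% and 17.30%.

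**Simulation.** 60 per arm with equal stratum sizes across arms; visits at Days 8, 15, 29, 43 and 57, with 10, 25, 55, 80 and 100% of the Week 8 cumulative response reached; 10% withdrawal spread over visits; two-sided 5% log-rank test with hypergeometric variance. Repeat runs move the gains by about 0.2 point.

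| Comparison, 50% mild | r = 1 | r = 2 | r = 4 | r = 8 |
|---|---|---|---|---|
| 17.07% vs 10.81%, gain in power (points) | about 0 | 0.4 | 1.4 | 2.6 |
| 20.93% vs 10.81%, gain in power (points) | about 0 | 1.0 | 2.6 | 4.5 |

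For scale, one run at 17.07% vs 10.81% gave power of 15.1, 14.9 and 14.3% unstratified against 15.6, 16.2 and 16.7% stratified, for r = 2, 4 and 8.

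**Null.** With both arms at 10.81%, 50% mild and r = 2 to 8, type I error is about 4.2% to 4.7% unstratified and about 4.8% to 4.9% stratified.

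**Sensitivity.**

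- *Mild share.* At 17.07% vs 10.81% and r = 8, the gain is 4.8 points with 70% mild and at most 1.3 with 30% mild.
- *Visit pattern.* The common pattern puts the 1% group at 0.55 × 20.93 = 11.5% by Week 4, below its reported 20.93%. With assumed arm-specific curves that match both the Week 4 and Week 8 rates, the gain for the 1% group is 1.4, 4.8 and 8.4 points at r = 2, 4 and 8.
- *Strata not balanced and not prognostic.* Stratifying loses 0.2 point at 17.07% vs 10.81%. The largest loss in any run was about 0.5 point (65.1% to 64.6%, with 14.63% vs 2.70% entered as Week 8 rates).

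**The case against.** The strongest case is that this is a preference and not a defect. The unstratified test is valid and errs only towards caution. SAP 9.4 and Protocol 11.3.8 require baseline IGA only for the CMH test, so SAP 9.2.10 departs from nothing. The same response is already tested with stratification at all five visits and analyzed within mild and moderate separately (SAP 9.5). No decision rests on this p-value, and stratifying it puts an adjusted p-value beside unadjusted curves and medians. All of that stands. It sets the priority low, but it does not make the change unsound.

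A second objection also stands: the size rests on assumptions. Mild share, stratum ratio and visit pattern are all missing from the documents. Dynamic allocation that also balances site does not guarantee equal stratum sizes, and with strata drawn at random the gain at 17.07% vs 10.81% fell to 0.5 point at an odds ratio of 4 and 1.2 at 10.

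Stronger readings that a reader might infer are not supported:

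- *The SAP contradicts itself or breaks its own adjustment rule.* It does not, because the rule covers the CMH test only.
- *False positives are inflated.* The unstratified error rate stays below 5% in these null scenarios.
- *Dropping the logistic regression leaves IGA without adjustment.* The CMH test and the mixed model still provide it.
- *The sample-size rates show a negligible gain.* Entering 2.70% as vehicle response by Week 8 conflicts with the 10.81% reported at Week 8.

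**Conclusion.** The point holds as a low-priority improvement. The log-rank test omits a factor that the trial allocates by and uses for the same response elsewhere; including it would usually help and would rarely cost anything noticeable.

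The direction is firm only if baseline IGA is prognostic. The size is illustrative: about 0.4 to 2.6 points of power for the 0.3% comparison and 1.0 to 4.5 for the 1% comparison, at 50% mild and ratios of 2 to 8. These figures carry foreign-trial rates over to this trial and use visit rates as minimum cumulative rates. They are not bounds: a higher mild share, a stronger contrast or earlier response in the active arm raises them, and no contrast brings them to about zero. The primary conclusion is unaffected in every case.

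**What to change.** - **SAP 9.2.10:** state that the log-rank test is stratified by baseline IGA (mild or moderate). Keep the curves, numbers at risk and medians by treatment group as planned.
- **Figure CF-3.1:** add a footnote that the p-value is stratified while the curves and medians are not.
- **SAP 9.2.11:** the VRS analysis follows the IGA one, so state that the strata apply to the IGA test only.

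Trial site should not be added as a stratum: the CMH test does not use it, and SAP 13.1 notes many sites with limited numbers per group. The censoring rule and the analysis set stay as they are.

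The cost is one sentence, one clause and one footnote, settled before database lock so that the choice is prespecified. No protocol text on the test changes. SAP 13.1 needs a line only if the sponsor chooses to log the added log-rank test there. The downsides are the mixed display and a possible loss of up to about 0.5 point if baseline IGA is not prognostic and the strata are unbalanced. If the sponsor prefers the unstratified test, a statement that this is deliberate would also settle the point.

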1.2.2.4 Phase 2 Trial in AD Patients Outside Japan (271-12-205)

In the phase 2 trial in AD patients (aged 10-70 years old) outside Japan, the efficacy, safety, and pharmacokinetics of the 8-week twice-daily multiple doses of OPA-15406 ointment was investigated by selecting 0.3% and 1% formulations (40 subjects for each group) for which the efficacy was suggested in the phase 1 trial in the US. The primary efficacy endpoint was established as the incidence of success in IGA (percentage of subjects with IGA score of 0 or 1 with improvement by at least 2 grades) at Week 4, and the incidence of success in IGA was 14.63%, 20.93%, and 2.70% in the 0.3% OPA-15406 group, the 1% OPA-15406 group, and the vehicle group, respectively. The 0.3% OPA-15406 group showed a higher incidence of success in IGA than in the vehicle group; however, no significant difference was observed between the groups ($p = 0.0690$, CMH test). In the 1% OPA-15406 group, a significant difference was observed in the incidence of success in IGA compared to the vehicle group ($p = 0.0165$, CMH test). Discontinuations due to adverse events occurred with 4 subjects (9.8%), 3 subjects (7.0%), and 7 subjects (18.9%) in the 0.3% OPA-15406 group, the 1% OPA-15406 group, and the vehicle group, respectively. Serious adverse events were reported as liver function test abnormal and multiple sclerosis in 1 subject each in the 0.3% OPA-15406 group, and giardiasis and depression in 1 subject each in the 1% OPA-15406 group; however, all of these events were determined as not IMP-related. In the results of clinical laboratory tests, vital signs, and 12-lead ECG, no marked difference was observed among the 3 groups. The plasma OPA-15406 concentrations at 4 hours post-administration at Week 4 were 0.236 to 7.26 ng/mL in 5 subjects in the 0.3% OPA-15406 group and 0.469 to 1.22 ng/mL in 4 subjects in the 1% OPA-15406 group.

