Usually, topical drugs for AD are evaluated for their efficacy once in 1 to 2 weeks, and if no improvements are observed within a month, the patient is generally considered for referral to a more specialized institution. Thus, Week 4 is established as an assessment point of the primary efficacy endpoint, and the treatment is also to be continued after Week 4 to assess the efficacy and safety thereafter. In the phase 2 trial in AD patients outside Japan (271-12-205), the incidence of success in IGA at Week 8 was 17.07%, 16.28%, and 10.81% in the 0.3% OPA-15406 group, the 1% OPA-15406 group, and the vehicle group, respectively. The incidence of success in IGA was higher in the 0.3% and 1% OPA-15406 groups than in the vehicle group, while no significant difference was observed. Also, no particular safety concerns were identified with the 0.3% and 1% formulations of OPA-15406. In this trial, the duration of treatment is established as 8 weeks to assess the efficacy and safety of the IMP in Japanese patients up to Week 8 and to compare the results with those of the phase 2 trial outside Japan (271-12-205).

Accordingly, it was judged scientifically and ethically appropriate to conduct this trial.

See the investigator's brochure for further details of data mentioned in this protocol and other trial results.

2 Trial Objectives

Primary objective: To evaluate Week 4 efficacy of OPA-15406 (0.3% and 1%) compared to the vehicle when administered twice daily for 8 weeks using incidence of success in Investigator's Global Assessment (IGA) as the primary endpoint in AD patients.

Secondary objective: To evaluate the safety of OPA-15406 (0.3% and 1%) when administered twice daily for 8 weeks in AD patients.

3 Trial Plan

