11.5 Rationale for Target Number of Patients

In the phase 2 trial outside Japan (271-12-205), the primary variable of incidence of success in IGA was 20.93% and 2.70% in the 1% OPA-15406 group and the vehicle group, respectively. In the present trial, with the assumption that the difference in the incidence of success in IGA between the vehicle group and the 1% OPA-15406 group is similar to that obtained in the foreign trial, a sample size of 54 subjects per group at a two-tailed 5% level of significance was calculated with at least an 80% power. In consideration of possible discontinuations and dropouts, the number of subjects is established as 60 subjects per group.

12 Quality Control and Quality Assurance for the Trial

To ensure quality of the trial, trial sites, contract research organizations, laboratories performing clinical laboratory tests, and the sponsor will perform quality control for the trial according to their respective Standard Operating Procedures.

The audit division of the sponsor company will carry out audits within the company and, as necessary, at the trial site and contract research organizations or organizations entrusted to perform related activities, and check whether quality control of the trial is appropriately performed according to the Standard Operating Procedures.

13 General Items of Caution Pertaining to the Trial

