### 12.2 Rationale for the Number of Subjects

In the phase 2 trial outside Japan (271-12-205), the primary variable of incidence of success in IGA was 20.93% in the 1% OPA-15406 group and 2.70% in the vehicle group, respectively. In the present trial, with the assumption that the difference in incidence of success in IGA between the 1% OPA-15406 group and the vehicle group is similar to that obtained in the foreign trial, a sample size of 54 subjects per group at a two-tailed 5% level of significance was calculated with at least an 80% power. In consideration of possible discontinuations and dropouts, the number of subjects is established as 60 subjects per group.

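### Time to first IGA response has no between-arm effect estimate, and its one timing summary, the median, is very unlikely to be reached at the foreign-trial rates

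*SAP*

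**What the plan says.** SAP 9.2.10 defines the endpoint as days to the first IGA response. Non-responders are censored at their final IGA assessment. It plans a Kaplan-Meier cumulative response rate per group, plotted, with the number at risk. It adds "the p-value of the log-rank test comparing the vehicle group and each OPA-15406 group, and the time until one half of the subjects" have responded (the median). The sentence says these are given at each timepoint, without saying whether the log-rank test is repeated with follow-up cut at each visit. SAP 9.2.11 treats time to VRS response in the same way. Protocol 11.3.1.2 planned only Kaplan-Meier plots for both endpoints, and SAP 13.1 does not list the log-rank test or the median as additions.

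The planning rates come from foreign trial 271-12-205. At Week 4, "the incidence of success in IGA was 14.63%, 20.93%, and 2.70% in the 0.3% OPA-15406 group", the 1% group and vehicle respectively (Protocol 1.2.2.4). At Week 8, "the incidence of success in IGA at Week 8 was 17.07%, 16.28%, and 10.81% in the 0.3% OPA-15406 group", the 1% group and vehicle (Protocol 1.2.3). SAP 12.2 sizes the trial "with the assumption that the difference in incidence of success in IGA between the 1% OPA-15406 group and the vehicle group is similar" to the foreign result.

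**The concern.** A time-to-response endpoint should show whether the drug works sooner, and by how much. Here the only number describing timing is the median, which needs half of an arm to respond, and the planning rates are far below half. If the median is not reached, the endpoint reports curves and a p-value but no effect size.

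The p-value has a related weakness. In the foreign trial the 1% group was well ahead at Week 4, while most vehicle success appeared between Weeks 4 and 8. An unweighted log-rank test gives a late first response nearly the same weight as an early one, so late vehicle responses can offset early drug responses.

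SAP 13.1 names time to response among the analyses that make the protocol's logistic regression unnecessary, so the output is meant to carry some weight.

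**Working it through.** **1. The plan's own figure.** Protocol 11.5 states "a sample size of 54 subjects per group at a two-tailed 5% level of significance was calculated with at least an 80% power". For 20.93% against 2.70%, the exact power of the two-sided Fisher test is 80.2% at 54 per group and 79.1% at 53, so 54 is reproduced. It concerns the Week 4 primary endpoint; no power is stated for time to response. With an allowance for dropout, "the number of subjects is established as 60 subjects per group", and that is the size used below.

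**2. Cumulative first response by Week 8.** The published rates are response at each visit. Cumulative first response cannot fall, so it is at least the larger of the two rates and, from these two visits alone, at most their sum:

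- 1% group: 20.93% to 20.93 + 16.28 = 37.21%
- 0.3% group: 17.07% to 14.63 + 17.07 = 31.70%
- vehicle: 10.81% to 2.70 + 10.81 = 13.51%

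Responses seen only at Weeks 1, 2 or 6 could raise these bounds; the documents do not report them.

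**3. The median.** With all 60 subjects followed to Week 8, it requires at least 30 responders. For X ~ Binomial(60, p), P(X ≥ 30) is 6 × 10⁻⁷ at p = 20.93%, 0.0009 at 30% and 0.029 at 37.21%. The other two arms have lower upper bounds, so their chances are smaller.

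**4. Shape of the effect.** Among vehicle non-responders at Week 4, (10.81 − 2.70)/(100 − 2.70) = 8.3% respond by Week 8, against 2.70% in the first four weeks. The 1% group has the same late risk if 0.083 × 79.07 = 6.6% of its subjects first respond after Week 4. With fewer, the hazards cross. At the upper bound of 16.28% its late risk is 16.28/79.07 = 20.6%. The risk ratio then falls from 20.93/2.70 = 7.8 in Weeks 0 to 4 to 20.6/8.3 = 2.5 in Weeks 4 to 8.

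**5. Power.** Simulated with 60 per arm, two-sided 5%, and first responses at Days 8, 15, 29, 43 and 57. Assumed, because not documented: 20% and 55% of the Week 4 value is reached by Weeks 1 and 2, and Week 6 is midway between Weeks 4 and 8. Vehicle is 10.81% by Week 8.

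| 1% group, first response after Week 4 | Cumulative by Week 8 | Log-rank, 8 weeks | Restricted mean to Day 57 | Gain, points |
|---|---|---|---|---|
| 0% | 20.93% | 37% | 84% | 47 |
| 4.07% | 25% | 59% | 88% | 30 |
| 9.07% | 30% | 79% | 91% | 12 |
| 14.07% | 35% | 92% | 94% | 1 |
| 16.28% | 37.21% | 95% | 94% | −1 |

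With vehicle at 13.51%, the gain is 59, 24 and 5 points at 20.93%, 30% and 37.21%. For the 0.3% group against vehicle at 10.81%, it is 39, 24, 12 and −6 points at 17.07%, 22%, 25% and 31.70%. With 15% dropout, the 1% gains at 20.93% and 30% are 44 and 12. An early-weighted log-rank test (Fleming-Harrington 1,0) recovers only 0 to 6 points. A log-rank test cut at Week 4 has 92% power. The log-rank test keeps its size under the null.

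**6. The restricted mean can be estimated at these rates.** Mean days gained by Day 57 = Σ (proportion first responding at visit j) × (57 − day j).

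- 1% group, first row: 0.0419 × 49 + 0.0733 × 42 + 0.0942 × 28 = 7.77 days
- vehicle: 0.0054 × 49 + 0.0095 × 42 + 0.0122 × 28 + 0.0406 × 14 = 1.57 days
- difference: 6.2 days

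In the last row, 0.0814 × 14 = 1.14 days is added, giving 7.3. The measure moves little over the undocumented range.

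**The case against.** The strongest reply is that the early effect is already well covered. SAP 9.1 and 9.2.1 give a CMH test and a Mantel-Haenszel risk difference with 95% CI at Weeks 1, 2, 4, 6 and 8, and Week 4 is the primary test. Kaplan-Meier rates are plotted. SAP 6.6.1 makes the secondary p-values a reference indication only. All of this stands. A reader might infer that time to response is judged by nothing but a p-value and a median, or that an early effect would go unseen; the documents do not support either. The by-visit analyses measure response at a visit, however, not time to first response.

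Second, a reader might infer from the Week 8 rates that vehicle largely catches up. That treats visit-level rates as first-response curves. The gap narrows from 18.23 to 5.47 points, but 4.65 of those 12.76 points come from the 1% group falling from 20.93% to 16.28%, which does not undo a first response. On the first-response scale the Week 8 gap is at least 20.93 − 10.81 = 10.12 points, or 7.42 with vehicle at 13.51%. The vehicle rise is also small in numbers: the percentages fit 1/37 and 4/37. SAP 12.2 assumes similarity for the Week 4 primary variable, not for any Week 8 pattern.

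Third, the log-rank sentence may mean a test cut at each visit, and at Week 4 that would lose nothing. This is a fair reading, and the text should settle it.

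Fourth, part of the gain comes from the horizon: a restricted mean to Day 57 gives no weight to responses first seen on Day 57. Ending the log-rank test at Week 6 raises its power from 37% to 66% in the first row. Under proportional hazards the restricted mean is the weaker test: with vehicle at 10.8% by Week 8 and hazard ratios of 2 to 3, log-rank power is 31% to 73% against 24% to 57%. These points argue for keeping the log-rank test, not against adding an estimate.

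**Conclusion.** The point holds in a limited form. SAP 9.2.10 has no between-arm effect estimate with a confidence interval, and the median is very unlikely to be reached in any arm: the chance is at most about 3% at the 37.21% bound. This assumes response rates like the foreign trial's. Japanese rates could be higher, so a stronger statement that the median cannot be estimated would go too far.

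The power loss is conditional. Against vehicle at 10.81%, it runs from about 47 points if no 1% subject first responds after Week 4 to none if about 16% do. The documents do not give this figure, so no fixed loss can be claimed. From the Week 4 and Week 8 rates alone, the no-loss end requires that no Week 4 responder is still a responder at Week 8 (37.21 = 20.93 + 16.28); responses seen only at other visits would relax that.

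The primary conclusion and type I error are unaffected. The case for a change rests on the missing effect measure and does not depend on the power figures.

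**What to change.** - **SAP 9.2.10.** Keep the Kaplan-Meier curves and the log-rank p-value, and state whether the log-rank test is cut at each visit or run once over 8 weeks. In place of the median, or beside it, report the difference in restricted mean time to first response to Day 57 between each OPA-15406 group and vehicle, with two-sided 95% CI, and name it as the effect measure. State what is done if an arm's longest follow-up ends before Day 57, since the Week 8 visit may fall 3 days early.
- **SAP 9.2.11.** Set a separate horizon for VRS within its 7-day collection period; Day 57 cannot carry over.
- **SAP 13.1.** List the log-rank, median and restricted-mean analyses, because the protocol planned only plots.
- **SAP 16.2.** Add an output for the estimate; only Kaplan-Meier plots are listed for these endpoints.

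The cost is SAP wording, a few lines of code and one more output, with no new data or subjects. The drawback is a restricted-mean test that is less powerful if hazards are proportional, which is why the log-rank test stays.
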